4. SELECTION AND WITHDRAWAL OF SUBJECTS

4.1. Subject Inclusion Criteria

Only subjects who meet all of the following criteria will be eligible for inclusion:

- 1. Healthy adult males and/or females (of non-childbearing potential), 18 to 55 years of age (inclusive) at the time of Screening.
- 2. Body mass index (BMI) within 18.0 to 35.0 kg/m², inclusive (minimum weight of at least 50.0 kg at Screening).
- 3. Medically healthy without clinically significant abnormalities at the screening visit, including physical examination and vital signs within the following ranges: heart rate 50 to 100 bpm, systolic blood pressure 100 to 149 mmHg; diastolic 70 to 94 mmHg.
- 4. The mean QTcF interval duration ≤450 msec for males and ≤470 msec for females measured from triplicate ECGs taken at least 1 minute apart with QT wave corrected for heart rate (HR) using Fredericia's method.
- 5. Hemoglobin/hematocrit, white blood cell (WBC) count, and platelet count equal to or greater than the lower limit of normal range of the reference laboratory (may be confirmed upon repeat testing without Sponsor approval).
- 6. Non-smokers (including tobacco, e-cigarettes, or marijuana), and no use of any tobacco product for at least 1 month prior to admission in the study.
- 7. Willing and able to provide written informed consent.
- 8. Willing and able to comply with all study assessments and adhere to the protocol schedule.
- 9. Have suitable venous access for blood sampling, as determined by an Investigator at screening.
- 10. If female, be of non-childbearing potential (e.g. post-menopausal as demonstrated by follicle stimulating hormone (>40 mIU/mL), amenorrhea for at least one year or surgically sterilized by tubal ligation, hysterectomy, bilateral oophorectomy and/or salpingectomy). Site personnel's review of the subject's medical records, medical examination, or medical history interview is acceptable evidence of female sterilization, verbal confirmation is adequate.

Confidential and Proprietary

Page 31 of 62

If male, willing not to donate sperm from the time of first study drug administration until 90 days after the final administration of study drug. If male and not intending to engage in sexual intercourse over the duration of the study, willing to agree to abstinence at screening. If male and engaging in sexual intercourse, willing to use a double barrier method of contraception (condom and spermicide). The latter criterion applies to all males (and/or female partners) including males who are surgically sterile and must be followed from the time of first study drug administration until 90 days after the final administration of study drug.

4.2. **Subject Exclusion Criteria**

Subjects will be excluded from the study if they meet any of the following criteria:

- 1. History or presence of significant cardiovascular (including arrhythmia and ventricular tachyphylaxis), pulmonary, hepatic, renal, hematological, gastrointestinal, endocrine, immunologic, dermatologic, or neurological disease, including any acute illness or surgery within the past 3 months determined by an Investigator to be clinically relevant.
- 2. Creatinine, blood urea nitrogen (BUN), alanine aminotransferase (ALT) and aspartate aminotransferase (AST) equal to 1.5 × upper limit of normal for the reference laboratory (may be confirmed upon repeat testing).

- Positive urine drug/alcohol testing at Screening or Day -1. 6.
- 7. Positive test results for HIV-1/HIV-2 Antibodies, Hepatitis B surface Antigen (HBsAg) or Hepatitis C Antibody (HCVAb).
- Positive test results for COVID-19 (PCR or Antibodies). 8.
- 9. History of substance abuse or alcohol abuse (defined as greater than 2 standard drinks per day) within the previous 2 years.

- 10. Use of any prescription medication or any over-the-counter medication, including herbal products and vitamins within 14 days or 5 half-lives (whichever is longer) prior to randomization.
- 11. Documented hypersensitivity reaction or anaphylaxis to any medication.
- 12. Blood donation (excluding plasma donation) of approximately 500 mL within 56 days prior to Screening, or receipt of a blood transfusion within 1 year of Screening.
- 13. Plasma donation within seven days prior to screening
- 14. Dosed in another investigational clinical trial within 30 days prior to Screening.
- 15. Any condition or prior therapy, e.g., seizures, or head trauma, that may lead to CNS effects during the study.
- 16. Documented or self-reported history of orthostatic hypotension or symptoms of hypotension such as dizziness, syncope, or blurred vision upon standing.
- 17. Any condition which is associated with increased brain permeability, e.g., cerebral ischemia, brain trauma, multiple sclerosis, brain tumors, brain infection.

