- History or presence of significant cardiovascular (including arrhythmia and ventricular tachyphylaxis), pulmonary, hepatic, renal, hematological, gastrointestinal, endocrine, immunologic, dermatologic or neurological disease, including any acute illness or surgery within the past 3 months determined by an Investigator to be clinically relevant.
- 2. Creatinine, blood urea nitrogen (BUN), alanine aminotransferase (ALT), and aspartate aminotransferase (AST) equal to 1.5 × upper limit of normal for the reference laboratory (may be confirmed upon repeat testing).
- 3. History of orthostatic reactions.
- 4. Orthostatic reaction at screening defined as drop in systolic blood pressure by ≥20 mmHg or drop in systolic blood pressure to <90 mmHg on standing for 3 minutes from the supine position.
- 5. History of seizure disorders, except for non-complex febrile seizures in childhood with absence of non-febrile seizures in parents and siblings.
- 6. Positive urine drug/alcohol testing at Screening or Day –2.
- 7. Positive test results for HIV-1/HIV-2 Antibodies, Hepatitis B surface Antigen (HBsAg) or Hepatitis C Antibody (HCVAb).
- 8. Positive test results for COVID-19 (PCR or Antibodies)
- 9. History of substance abuse or alcohol abuse (defined as greater than 2 standard drinks per day) within the previous 2 years.
- 10. Use of any prescription medication or any over-the-counter medication, including herbal products and vitamins within 14 days or 5 half-lives (whichever is longer) prior to randomization.
- 11. Documented hypersensitivity reaction or anaphylaxis to any medication.
- Blood donation (excluding plasma donation) of approximately 500 mL within 56 days prior to 12. Screening, or receipt of a blood transfusion within 1 year of Screening.
- 13. Plasma donation within seven days prior to screening.
- 14. Dosed in another investigational clinical trial within 30 days prior to Screening.
- Any condition or prior therapy, e.g., seizures, or head trauma, that may lead to CNS effects during 15. the study.
- 16. Documented or self-reported history of orthostatic hypotension or symptoms of hypotension such as dizziness, syncope, or blurred vision upon standing.
- Any condition which is associated with increased brain permeability, e.g., cerebral ischemia, 17. brain trauma, multiple sclerosis, brain tumors, brain infection.

Investigational Product, Dosage and Mode of Administration:

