3.1.2. General

Eligible subjects will be scheduled to return to the clinic and be admitted for a confinement period of 3 days in the SAD. The confinement period will begin the day before the start of study

drug administration to confirm eligibility for the study and for the completion of baseline assessments.

Subjects will return to clinic on Day 8 ± 2 days for the Follow-Up visit.

Safety and tolerability of each regimen will be assessed by adverse event (AE) monitoring, clinical laboratory tests, vital signs, body weight, electrocardiograms (ECGs), and physical examinations. Enrollment into Cohorts 2 through 5 will commence after all subjects in the prior cohort have completed the Follow-Up visit, and safety and PK data from all prior cohorts have been reviewed by a Data Monitoring Committee (DMC) consisting of the Principal Investigator, a medical representative from the Sponsor, and a PK expert, and no clinical concerns are identified.

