3.3. Treatment Assignment

Subjects who meet all criteria for enrollment will be randomly assigned to 1 of 2 treatment groups, ST-2427 or placebo, following a 4:2 allocation. A randomization schedule will be produced by an unblinded statistician using a validated computer program. Once baseline data (Day –1) has been reviewed and subjects are determined to be eligible for the study, they will be assigned a unique randomization number. Investigators and subjects will remain blinded to the study drug assignment and only certain designated staff (such as pharmacy personnel) will be unblinded to study treatment.

Sealed code break envelopes will be provided by an unblinded statistician prior to the start of the study. During the study, the blind is to be broken by an Investigator only when subject safety is at risk and unblinding must occur to determine effective medical intervention for the subject. All unscheduled unblinding events must be reported to the medical monitor and SiteOne Therapeutics, Inc. as soon as possible.

[figure not shown]

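### Exclusion criterion 2 applies only at exactly 1.5 × ULN; as written, it does not exclude higher creatinine, BUN, ALT or AST

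*Combined protocol and SAP*

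**What the plan says.** Section 4.2, exclusion 2, names creatinine, BUN and ALT and then reads "aspartate aminotransferase (AST) equal to 1.5 × upper limit of normal for the reference laboratory", with a note that the result may be confirmed by repeat testing. The synopsis has the same comparator: "and aspartate aminotransferase (AST) equal to 1.5 × upper limit of normal for the reference laboratory". Neither place adds a word or symbol for values above the limit.

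The companion laboratory criterion, inclusion 5 in section 4.1, does give a direction: "platelet count equal to or greater than the lower limit of normal range of the reference laboratory".

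Three other provisions bear on renal and hepatic status, none with a numeric limit for these analytes:

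- Inclusion 3 (section 4.1) asks that subjects be "Medically healthy without clinically significant abnormalities at the screening visit".
- Exclusion 1 (section 4.2) covers "History or presence of significant cardiovascular (including arrhythmia and ventricular tachyphylaxis), pulmonary, hepatic, renal, hematological" and other disease.
- Sections 3.1.2 and 3.3 place an eligibility check before dosing. Confinement starts the day before, "to confirm eligibility for the study and for the completion of baseline assessments", and once the Day -1 baseline data "has been reviewed and subjects are determined to be eligible for the study, they will be assigned a unique randomization number".

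**The concern.** An exclusion set at a multiple of the upper limit of normal is presumably meant to keep out raised values. With a bare equality it does not. A subject at 2 × ULN does not meet criterion 2, while a subject at exactly 1.5 × ULN does.

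Two further points stay open even for a reader who infers an upper limit: whether the bound itself excludes, and whether one analyte suffices or all four must meet it. The lead-in to section 4.2 says that meeting any criterion excludes, but that works across criteria and does not settle the *and* inside criterion 2.

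Section 2.1 describes this as the first-in-human study, and its primary objective is safety and tolerability. Under section 6.5 each cohort has four subjects on ST-2427, so one subject with raised entry values is 1/4 = 25% of the active data that the DMC sees for that dose. Section 9.5 requires protocol deviations to be recorded. Read literally, enrolling a subject above 1.5 × ULN is not a deviation from criterion 2, so it need not be captured as one.

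**Working it through.** The plan gives no figure to reproduce. The check compares wording, followed by a short illustration.

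**1. How the numeric laboratory, ECG and vital-sign limits are written**

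| Criterion | Form of the limit |
|---|---|
| Inclusion 3 (heart rate, blood pressure) | ranges |
| Inclusion 4 (QTcF) | ≤ |
| Inclusion 5 (hemoglobin/hematocrit, WBC, platelets) | at or above the lower limit of normal |
| Inclusion 10 (FSH, given as an example) | > |
| Exclusion 4 (orthostatic reaction; visible in the synopsis only) | ≥ and < |
| Exclusion 2 (creatinine, BUN, ALT, AST) | equality only |

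Exclusion 4, for instance, begins "Orthostatic reaction at screening defined as drop in systolic blood pressure by ≥20 mmHg". Exclusion 2 is the only one of these limits written as a bare equality. Exclusions 6 to 8 are positive/negative tests and need no operator.

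**2. Could a symbol have been lost in reading the PDF?** This is unlikely. The comparator is spelled out in words in both places, and symbols such as ≥ and < survive nearby in the synopsis.

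**3. The literal rule.** Exclude if result = 1.5 × ULN:

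- 1.49 × ULN: not excluded
- 1.50 × ULN: excluded
- 1.51 × ULN: not excluded
- 3.0 × ULN: not excluded

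**4. Does the repeat-test clause rescue it?** It points the other way. Under equality, a repeat result above 1.5 × ULN would fail to confirm the exclusion. The clause makes sense only for a one-sided limit, which suggests that words were dropped.

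**5. How many reportable results can exclude?** At most one per analyte, and none where 1.5 × ULN falls between reportable values. The documents give no ULN or reporting precision, so the following rests on assumed whole-number ULNs and whole-number results:

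- ULN 40: 1.5 × 40 = 60. A result of 60 excludes; 61 does not.
- ULN 45: 1.5 × 45 = 67.5. No result excludes.
- ULN from 30 to 60 (31 values): 1.5 × ULN is whole only for an even ULN. That gives 16 ULNs with one excluding result and 15 with none.

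This shows how narrow an equality rule is. It says nothing about how often raised values would occur in this trial. If *and* is read jointly, all four analytes would have to equal their own 1.5 × ULN at once.

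**6. Does another criterion set a numeric limit?** None does. Inclusions 1 and 3 and exclusion 1 turn on whether the subject is healthy, an abnormality is clinically significant or a disease is significant. The Day -1 review applies the same criterion 2 text.

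**The case against.** The best case against is that this is a drafting slip with one sensible reading. Nobody sets an exclusion at a multiple of an upper limit in order to admit higher values, and a single experienced site would very likely treat it as an upper bound. A subject with markedly raised values should also fail inclusion 3 or exclusion 1, and enrolling someone with a clinically significant abnormality would still breach inclusion 3. Section 4.3 lets the investigator or sponsor discontinue a subject for safety or ineligibility. The whole-number ULN illustration describes nothing specific to this trial. Section 12.1 requires IRB/IEC re-approval of amendments, and the protocol is already at Amendment 3, dated 25 June 2021, after the estimated first enrolment in April 2021.

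Most of this stands as a limit on the consequences. The likely reading and the judgement-based safeguards make the practical effect small, the illustration is only that, and the timing argues against an amendment for this alone. None of it corrects the text, supplies another numeric limit, or answers whether the bound is included and whether one analyte suffices.

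**Conclusion.** The concern holds: exclusion criterion 2 is wrong as written, in both places where it appears. Its literal effect is to exclude at one point and leave every higher value to investigator judgement, although it is the only numeric renal or hepatic entry limit in the protocol.

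The frequency of values above 1.5 × ULN cannot be estimated from the documents, and the practical effect is probably small. Sample size, populations and planned analyses are unaffected. What is lost is an entry limit that can be enforced and audited. It should be corrected.

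The conclusion assumes that the extracted wording matches the PDF. It does not depend on the assumed ULNs.

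**What to change.** In section 4.2 and in synopsis exclusion 2, replace the bare equality with the one-sided comparison that the sponsor intends. The sponsor should confirm whether a result exactly at the bound excludes, and state whether any single analyte meeting the limit is enough. Use identical wording in both places. The limit itself is a clinical matter for the sponsor, and no value is proposed here.

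The cost is a few words in two places. Table 4 already schedules clinical chemistry and the inclusion/exclusion review at Screening and Day -1, so no test, visit or text on timing is added. Because amendments need IRB/IEC re-approval, it is proportionate to include the change in the next one.

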4.3. Subject Withdrawal Criteria

There are no protocol-defined withdrawal criteria.

Subjects have the right to withdraw from the study at any time and for any reason without prejudice to their future medical care by the Investigator or at the institution. Subjects may also be discontinued from the study by the Investigator or the Sponsor for reasons such as safety, non-compliance, or ineligibility.

The Investigator will make a reasonable effort to determine the reason for withdrawal while respecting the subject's rights.

Reasons for removal from investigational product or observation might include:

- withdrawal of consent
- administrative decision by the Investigator or Sponsor
- hardship (e.g., move, family situation, change in job, etc.)
- pregnancy

Confidential and Proprietary

Page 33 of 62

- ineligibility
- major protocol deviation
- subject noncompliance
- AE
- death

Reasons for withdrawal will be reported in the corresponding CRF. Withdrawal of consent should only be indicated if no more specific reason can be ascertained.

For all subjects withdrawing from the study prior to the end of the study, a complete final evaluation including the assessments defined for the Follow-up visit should be made at the time of the subject's withdrawal.

5. TREATMENT OF SUBJECTS

5.1. **Description of Study Drug**

Table 5: **Investigational Product**

	Investigation	onal Product
Product Name:	ST-2427 for IV Infusion	Placebo (5% Dextrose Injection, USP)
Dosage Form:	Sterile Solution	Sterile Solution
Unit Dose (by Cohort)	250 mL total volume 1: 5 mg ST-2427 2: 10 mg ST-2427 3: 15 mg ST-2427 4: 22 mg ST-2427 5: 33 mg ST-2427	0 mg/mL
Route of Administration	Intravenous Infusion	Intravenous Infusion
Physical Description	Clear, colorless solution	Clear, colorless solution
Manufacturer	AMRI, Albany, NY Sterile solution will be prepared by Alta Sciences	Sourced by Alta Sciences

5.2. Concomitant Medications

No concomitant therapy is allowed between the start of confinement through the completion of the Follow-up visit. In addition, subjects are disqualified from participation in this study if they used any prescription medication or any over-the-counter medication, including herbal products and vitamins within 14 days or 5 half-lives (whichever is longer) prior to randomization.

5.3. **Treatment Compliance**

All study drug will be administered to all subjects by qualified site personnel during the confinement period. As such, treatment compliance is not relevant to this study. Missed doses will be assumed to be for reasons of subject safety, withdrawal, dosing error or other protocol deviation.

5.4. Randomization and Blinding

Subjects who meet all criteria for enrollment will be randomly assigned to 1 of 2 treatment groups, ST-2427 or placebo, following a 4:2 allocation. A randomization schedule will be produced by an unblinded statistician using a validated computer program. Once baseline data has been reviewed and subjects are determined to be eligible for the study, they will be assigned a unique randomization number. Investigators and subjects will remain blinded to the study drug assignment and only certain designated staff (such as pharmacy personnel) will be unblinded to study treatment.

Sealed code break envelopes will be provided by an unblinded statistician prior to the start of the study. During the study, the blind is to be broken by an investigator only when subject safety is at risk and unblinding must occur to determine effective medical intervention for the subject. Any unblinding events must be reported to the medical monitor and SiteOne Therapeutics, Inc. as soon as possible.

After all Follow-Up assessments are complete for subjects in a given cohort, safety and PK data will be reviewed by the DMC to determine whether to proceed to the next cohort, and the dose of ST-2427 to be administered in the next cohort.

In the event a pre-defined protocol stopping criterion is met, or a serious adverse event is observed for which knowledge of the randomization code would guide treatment decisions, the Investigator may be unblinded. In such cases, the Sponsor must be informed of the decision to unblind and provided all associated evidence within 24 hours.

Subjects who are randomized but withdraw prior to participation in the study will be replaced. Subjects that withdraw consent prior to dosing or discontinue due to adverse events or stopping criteria may be replaced.

Page 36 of 62

Confidential and Proprietary

6. STUDY DRUG MATERIALS AND MANAGEMENT

6.1. **Study Drug**

The study drug substance (ST-2427) will be manufactured by AMRI, Albany, New York in accordance with current good manufacturing practices (GMPs).

The placebo, Sterile 5% Dextrose Injection, USP (D5W) will be obtained commercially by the study site.

6.2. **Study Drug Packaging and Labeling**

Study drug substance (ST-2427) will be supplied to the pharmacy at the study site as non-sterile drug substance powder. Study drugs will be labeled according to the local regulatory requirements.

6.3. **Study Drug Storage**

ST-2427 will be stored frozen at -20°C, protected from light.

The D5W will be stored and handled according to the manufacturer label.

6.4. **Study Drug Preparation**

ST-2427 for IV infusion sterile solutions will be prepared by the clinical site pharmacy. The drug substance will be reconstituted in sterile 5% dextrose injection, USP. No other excipients will be added to the infusion solution. The site pharmacy will prepare the infusion solutions in a sterile compounding area and follow the requirements in USP <797> Pharmaceutical Compounding – Sterile Preparations.

Concentrations will be determined by the dose group and total volume of infusion. Refer to the Study Pharmacy Manual for detailed instructions.

6.5. Administration

Four subjects in each cohort will be randomized to receive ST-2427. ST-2427 will be administered via IV over 1 hour (\pm 10 minutes).

Two subjects in each cohort will be randomized to receive placebo. The placebo drug will be the matched volume of D5W administered via IV over 1 hour (± 10 minutes) to maintain the blind.

38

Page 37 of 62

6.6. Study Drug Accountability

Study drug will be stored, inventoried, reconciled, and destroyed according to applicable regulations.

6.7. Study Drug Handling and Disposal

Any remaining study drug will be returned to SiteOne Therapeutics, Inc. or its designee for destruction or destroyed by the site (if the site has appropriate facilities and written procedures to dispose of clinical trial materials).

[figure not shown]
Confidential and Proprietary Page 38 of 62

7. PHARMACOKINETIC ASSESSMENTS

Blood samples will be collected at protocol-defined time points for analysis of ST-2427 concentrations in whole blood using a validated analytical method. In addition, urine samples will be collected for analysis of ST-2427 concentrations in urine using a validated analytical method. A PK manual will be provided.

